### **6.4.2. Serum Creatinine**

Baseline serum creatinine (SCr) is defined in the same way as baseline eGFR (Section 6.4.1).

### **6.4.3. Safety Assessments**

Baseline for continuous safety assessments (i.e., vital sign assessments, weight, BMI, and laboratory measurements) is defined as the average value of measurements collected up through the date of, but not after, first study drug administration.

### **6.4.4. Urine Albumin to Creatinine Ratio**

Baseline ACR is defined as the last ACR value prior to the first study drug administration. Baseline ACR is summarized using the geometric mean of ACR values.

### **6.4.5. Natural log(ACR)/eGFR**

Baseline of natural log(ACR)/eGFR is defined as the ratio of the natural log of baseline ACR (Section 6.4.4) divided by baseline eGFR (Section 6.4.1).

### **6.4.6. Baseline Hematuria**

Presence of hematuria at baseline is defined as red blood cells per high power field (RBC/HPF) > 2 in two measurements prior to the first dose of study drug. If only one RBC/HPF measurement is available prior to the first dose of study drug, that measurement is used to determine baseline hematuria.

If no RBC/HPF measurements are available prior to the first dose of study drug, urine occult blood dipstick measurements is used to determine baseline hematuria. If the two occult blood measurements prior to the first dose of study drug result is not ‘trace’ or ‘negative’ (e.g., result is +1,+2, or +3), then the patient is considered to have baseline hematuria. If no RBC/HPF measurement is available and only one occult blood measurement prior to the first dose of study drug is available, then the patient is considered to have baseline hematuria if the results are not ‘trace’ or ‘negative’.

#### **6.4.7. Baseline Visual Impairment**

Patients with normal visual acuity are those with 20/20 vision or better (e.g., 20/15, 20/10, etc.) in both eyes. Any patient whose vision is worse than 20/20 in either eye is considered to have visual impairment.

#### **6.4.8. Baseline Audiology Impairment**

Patients with normal hearing are those with pure tone audiometry (PTA) < 25 decibels in both ears. Any patient with > 25 decibel hearing in either ear is considered to have audiology impairment.

### **6.5. Derived and Transformed Data**

#### **6.5.1. Age**

Subject’s baseline age is defined as the age at consent (Screen A). Subject’s age used for each eGFR calculation (Section 6.5.6) is the age on the date of each serum creatinine collection. Calculated age is rounded down to the nearest whole year and expressed as an integer:

- Age (year) = Floor ((visit date – date of birth)/365.25)

#### **6.5.2. Study Day**

Study day is the day relative to the date of randomization. Day 1 is defined as the date of randomization. Assessments that occur after randomization but before the first dose of study drug are considered to occur on study Day 1.

Assessments without time-stamp collected on the same date as the first date of study drug administration are considered to occur before the first dose of study drug administration.

For visits (or events) after randomization, day is calculated as:

- Study day = visit (or event) date - date of randomization + 1

For visits (or events) before randomization, day is calculated as:

- Study day = visit (or event) date - date of randomization

The quantity ‘days since first dose’ is defined as:

- days since first dose = visit (or event) date – date of first + 1

The quantity ‘days since last dose’ is defined as:

- days since last dose = visit (or event) date - date of last dose

For summaries that present distribution of time expressed in weeks and months, weeks are defined as days divided by seven and months as days divided by 30.4.

### 6.5.3. Change from Baseline

Change from baseline is calculated using the baseline value (Section 6.4) and the value closest to the target study day, using the rules defined in Section 6.5.4.

### 6.5.4. Visit Windows

Analysis visits and their windows are defined using derived study day (Section 6.5.2) instead of relying on visit labels in the clinical database because clinical visits may occur outside protocol-specified windows. Study day and days after last dose are calculated using the actual date of each scheduled and unscheduled assessment and compared to the target for each analysis visit as specified in Table 3 and Table 4. They are included in analyses of safety and efficacy as follows:

- Efficacy analyses for endpoints assessed at Week 48 or Week 100 use the analysis windows based on target study day in Table 3, irrespective of whether or not a patient is receiving treatment of study drug efficacy analyses for Week 100 will not include the Week 52 data.
- Efficacy analyses for endpoints assessed at Week 52 or Week 104 use the off-treatment analysis windows based on days after last dose in Table 3.
- Safety analyses use the analysis windows defined in Table 3 so long as the patient is receiving treatment of study drug. Safety follow-up at Week 52 will also be summarized according to Table 3 so long as the patient has not permanently discontinued treatment prior to Week 52. Similarly, safety follow-up at Week 104 is summarized according to Table 3 for patients completing treatment through Week 100. Once a patient permanently discontinues study treatment, safety data are summarized according to time since last dose as defined in Table 4.

If a parameter is assessed or measured more than once within a visit window, the one that is closest to the protocol-scheduled time point (i.e., target) is used for the purposes of data analysis and summary. If two assessments are equidistant from a target, the earlier assessment is used. If the visit used for analysis includes two assessments on the same day, the average of the two measurements is used.

Records from visits not closest to the target study day, and therefore not used in analyses, are presented in by-subject data listings.

**Table 3. Analysis Visit Windows**

Analysis Visit	Label	Target		Analysis Window
		Study Day a	Days After Last Dose	
0	Day 1 b	1	-	1
1	Week 1	7	-	$2 \leq \text{study day} \leq 10$
2	Week 2	14	-	$11 \leq \text{study day} \leq 21$

Analysis Visit	Label	Target		Analysis Window
		Study Day a	Days After Last Dose	
4	Week 4	28	-	$22 \leq \text{study day} \leq 35$
6	Week 6	42	-	$36 \leq \text{study day} \leq 49$
8	Week 8	56	-	$50 \leq \text{study day} \leq 70$
12	Week 12	84	-	$71 \leq \text{study day} \leq 126$
24	Week 24	168	-	$127 \leq \text{study day} \leq 210$
36	Week 36	252	-	$211 \leq \text{study day} \leq 294$
48	Week 48 c	336	-	$295 \leq \text{study day} \leq 350$
52	Week 52 d	-	28	$14 \leq \text{Days after last dose}^e \leq 35$
64	Week 64	448	-	$407 \leq \text{study day} \leq 490$
76	Week 76	532	-	$491 \leq \text{study day} \leq 574$
88	Week 88	616	-	$575 \leq \text{study day} \leq 658$
100	Week 100 f	700	-	$659 \leq \text{study day} \leq 714$
104	Week 104 g	-	28	$14 \leq \text{days after last dose}^h \leq 35$

a Study Day is relative to the date of randomization (Section 6.5.2).

b Day 1 is the last measurement prior to the first study drug administration.

c Week 48 is the end of the first-year dosing interval and should coincide with the last dose in the first year.

d Week 52 is the first-year dosing interval 4-week follow-up; must be after the last dose in the first year and before receiving treatment in the second year.

e Last dose for analysis visit 52 is the Week 48 dose or date of last dose for permanent study drug discontinuation prior to Week 48.

f Week 100 is the end of the second-year dosing interval and should coincide with the last dose in the second year.

g Week 104 is the second-year dosing interval 4-week follow-up; patient must have been dispensed treatment in the second year (i.e., Week 52), otherwise Week 104 is considered missing.

h Last dose for analysis visit 104 is the Week 100 dose or date of last dose for permanent study drug discontinuation after Week 52 and prior to Week 100.

#### 6.5.4.1. Off-Treatment Visit Windows

Patients who permanently discontinue study drug prior to Week 100 are asked to resume the planned assessments according to the study schedule in the protocol. Off-treatment values for clinical laboratory evaluations (Section 10.5), vital signs (Section 10.6), and electrocardiograms (Section 10.8) are those that occur after the last dose date for patients permanently discontinuing study drug prior to Week 100, and is summarized relative to their last dose of study drug. Off-treatment safety assessments are grouped for analyses according to the strategy in Table 4. Assessments that occur on the date of last dose are considered on treatment.

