## 10. SAFETY AND TOLERABILITY

Safety and tolerability are evaluated by AEs, SAEs, clinical laboratory test results, body weight, vital signs, 12-lead ECG findings, physical examination, visual acuity, and audiology assessment. All analyses of the safety data are performed using the safety analysis set.

Descriptive statistics are presented by treatment group assignment in the safety analysis set. No formal statistical testing is performed for safety analyses. Safety is also summarized by the subgroups defined in Section 8.3. On-treatment values are summarized according to the analysis study windows in Section 6.5.4; off-treatment values are summarized according to the analysis study windows in Section 6.5.4.1. Safety data summaries are grouped by treatment year.

Continuous safety parameters (including selected clinical chemistries and vital signs) may be summarized using the methodology described in Section 8.6.1, Section 8.7.1, Section 8.8.1, and Section 8.9.1. Only the visit windows outlined in Table 3 are included in these analyses.

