### 10.9. Visual Acuity

Patients with normal visual acuity are those with 20/20 vision or less (e.g., 20/15, 20/10, etc.) in both eyes. Findings from visual acuity examinations are listed. Observed logMAR value and its change from baseline are summarized descriptively by time point. In addition, shift tables are generated by treatment, visit, and normal versus abnormal visual acuity values.

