### 10.10. Audiology Assessment

Findings from audiology assessments are listed. The average pure-tone hearing threshold for each ear is measured using the automated pure tone test. Patients with normal pure-tone hearing are those with pure tone audiometry (PTA)  $< 25$  decibels in both ears. Any patient with  $\geq 25$  decibel hearing in either ear are considered to have audiology impairment. The number and percentage of patients with normal or impaired hearing in at least one ear is summarized by time point. In addition, number and percentage of patients within each of the following categories will be summarized at baseline, Week 48, and Week 100:

- PTA  $\leq 25$  dB
- 25 dB  $< PTA \leq 40$  dB (mild to moderate hearing loss)
- 40 dB  $< PTA \leq 70$  dB (moderate to severe hearing loss)
- 70 dB  $< PTA \leq 85$  dB (severe to profound hearing loss)
- PTA  $> 85$  dB (profound hearing loss)

Descriptive statistics for observed values and change from baseline in hearing threshold for each ear (i.e., right and left) are presented.

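### The hearing category table leaves out patients who stopped study drug, and the Week 100 hearing and vision tests of Year 1 stoppers reach no summary table

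*SAP*

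**What the plan says.** The SAP counts visual acuity and audiology as safety evaluations (criteria for evaluation in the summary; Section 10). The schedule of assessments (SAP Table 2) places them at Day 1, Week 48 and Week 100 or end of treatment. Patients who stop drug early are asked to carry on with the planned assessments (6.5.4.1), so the data are meant to exist.

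The rules for placing these values are:

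- **On treatment (6.5.4):** "Safety analyses use the analysis windows defined in Table 3 so long as the patient is receiving treatment of study drug".
- **After permanent discontinuation (6.5.4):** "Once a patient permanently discontinues study treatment, safety data are summarized according to time since last dose as defined in Table 4".
- **Safety section (10):** "off-treatment values are summarized according to the analysis study windows in Section 6.5.4.1".
- **Definition in 6.5.4.1:** "Off-treatment values for clinical laboratory evaluations (Section 10.5), vital signs (Section 10.6), and electrocardiograms (Section 10.8) are those that occur after the last dose". Sections 10.9 (visual acuity) and 10.10 (audiology) are not in that list. Later in the same section comes a general sentence: "Off-treatment safety assessments are grouped for analyses according to the strategy in Table 4".
- **Table 4:** windows run from 14 to 350 days after last dose. Its footnote counts values less than 14 days after last dose as on treatment.

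The displays are:

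- **Hearing categories (10.10):** five pure-tone categories that "will be summarized at baseline, Week 48, and Week 100". The normal/impaired hearing summary runs by time point.
- **Vision (10.9):** logMAR is summarised by time point, and "shift tables are generated by treatment, visit, and normal versus abnormal visual acuity values".

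**The concern.** A comparison of hearing at Week 48 and Week 100 that admits only patients still on drug is made in a group selected after randomisation. If a patient stopped because hearing or vision worsened, or if a loss persisted after stopping, the Week 48 and Week 100 columns would not show it. If stopping differs between arms, the arms are no longer compared like with like.

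The same on/off-treatment split applies to laboratory tests, vital signs and ECG, but some of those have other displays to fall back on. Laboratory parameters get baseline-to-end-of-treatment and worst-value shift tables (10.5.2), and abnormal ECG values are counted at any time during the study (10.8). Sections 10.9 and 10.10 specify nothing of that kind. With two scheduled post-baseline tests, one result that cannot be placed may be half of a patient's follow-up.

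**Working it through.** The plan gives no figure to reproduce here. The check is to map test day and last-dose day onto the windows.

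**Inputs.** Days since last dose = test date − date of last dose (6.5.2). Week 48: target day 336, window 295–350. Week 100: target day 700, window 659–714 (SAP Table 3); the COVID-19 addendum leaves the Week 100 window unchanged for patients who stopped before Week 100. SAP Table 4 windows: 14–35, 36–71, 72–99, 100–252 and 253–350 days. Year 1 dosing ends at Week 48 (day 336), and dosing restarts at Week 52 (day 364).

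**1. Who is in the Week 48 and Week 100 columns.** A value counts as on treatment if it is less than 14 days after last dose. For a test on day 336 that needs a last dose on day 323 or later (336 − 323 = 13). For a test on day 700 it needs day 687 or later (700 − 687 = 13). Anyone who stopped earlier is outside the column.

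**2. Example: last dose at Week 30 (day 210).**
- Week 48 test: 336 − 210 = 126 days, in the 24-week off-treatment window (100–252). It has a summary window, but not the Week 48 column.
- Week 100 test: 700 − 210 = 490 days, beyond 350. It has no window.
- If an end-of-treatment test were done on day 215, it would be 5 days after last dose and count as on treatment. By study day it belongs to Week 36 (211–294), which is not a column of the five-category table.

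**3. Where the gap begins.** A test on day T has a Table 4 window only if T − last dose ≤ 350.
- T = 700: last dose must be on day 350 or later. Every last dose up to day 336 gives at least 700 − 336 = 364 days, so none fits.
- Across the scheduled visit range of day 700 ± 3, the earliest test still gives 697 − 336 = 361 days.
- Across the full analysis window, the latest last-dose day without a window is 659 − 351 = 308 for the earliest test and 714 − 351 = 363 for the latest. A Year 1 stopper tested unusually early can therefore still be placed: for T = 659, last dose on days 309–336.

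**4. Where there is no gap.**
- Week 48: the largest possible interval is 350 − 1 = 349 days, so every such test has a place.
- Year 2 stoppers: with last dose on day 364 or later, 700 − 364 = 336 and 714 − 364 = 350, both inside Table 4.

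**5. Effect on the Week 48 and Week 100 hearing columns.** This cannot be estimated from the documents. An illustration on assumed values: let 10% of patients who stay on drug worsen, let a fraction s stop, and let stoppers have R times that risk. The rate in the whole arm is 0.10(1 − s) + 0.10·R·s, while the column shows 10%.

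| s | R = 1 | R = 2 | R = 3 |
|---|---|---|---|
| 10% | 10% | 11% | 12% |
| 20% | 10% | 12% | 14% |
| 30% | 10% | 13% | 16% |

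The table assumes that every stopper is tested and that none falls within the 14-day allowance. With R = 1 the distortion is nil.

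**The case against.** A reader might infer from the list in 6.5.4.1 that every hearing or vision loss in a patient who stopped is only listed, or that all hearing and vision tables hold only patients on drug. The documents do not support either reading.

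- Section 6.5.4, the grouping sentence in 6.5.4.1 and Section 10 send off-treatment safety data to Table 4 without limit by parameter. Section 10 names vision and hearing as safety evaluations, and addendum Section 4.5 includes both when it spells out the data it covers.
- The vision summaries and the normal/impaired hearing summary run by time point or visit, and Table 4 calls its rows analysis visits. They can hold off-treatment values. Only the five-category table is fixed to Week 48 and Week 100.
- Losses reported as adverse events are tabulated by arm, as treatment-emergent events or, with onset more than 30 days after last dose, as off-treatment events (10.1). Events leading to discontinuation have their own table (10.1.2).
- Safety is descriptive, without formal tests, and separating on-treatment from off-treatment values is a legitimate choice.

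All of this stands, and it confines the point to the five-category table, the omission in 6.5.4.1 and the end of Table 4. It does not remove those. Adverse event tables depend on a loss being reported and do not replace measured thresholds. Sections 10.9 and 10.10 name no Table 4 display. The 350-day limit holds however the list in 6.5.4.1 is read.

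**Conclusion.** The point holds in a limited form. By rule, the five-category hearing table leaves out patients who stopped, apart from values less than 14 days after last dose that also fall in the Week 48 or Week 100 window. The definition in 6.5.4.1 is out of step with the general rule, so a programmer could reasonably drop vision and hearing from the off-treatment summaries. The Week 100 test of a Year 1 stopper, done on or near day 700, enters no summary table on any reading; this limit affects every safety parameter, but weighs more on two assessments with so few scheduled tests.

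It should not be stated as a missing safety analysis. The Week 48 tests of stoppers, and the Week 100 tests of Year 2 stoppers, do have Table 4 windows. The size of any distortion is unknown: the documents give neither stopping rates nor the risk in patients who stop. This is a cheap improvement to the tables.

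**What to change.** 1. Add Sections 10.9 and 10.10 to the list in 6.5.4.1, so that the definition agrees with 6.5.4 and Section 10.
2. Extend Table 4 beyond 350 days, so that the Week 100 tests of Year 1 stoppers have a window.
3. In 10.9 and 10.10, add a Week 48 and Week 100 display by study day for all safety-population patients irrespective of treatment, with shift from baseline by arm. Section 6.5.4 already uses study day in this way for efficacy at these two visits. Keep the on-treatment display beside it.

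The cost is SAP wording and a few table rows; no new data are needed. The small downside is that some values in the added display are taken months after last dose, or more than a year after in the case of Week 100 tests in patients who stopped early in Year 1. Days since last dose should be shown with them.

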**Table 4. Analysis Visits for Off-Treatment Safety Analysis**

Off-Treatment Analysis Visit	Label	Target Study Day (days after last dose)	Analysis Window
0	Last dose (on-treatment) a	0	0
4	Off Treatment 4-weeks b	28	14 ≤ days after last dose ≤ 35
8	Off Treatment 8-weeks b	56	36 ≤ days after last dose ≤ 71
12	Off Treatment 12-weeks b	84	72 ≤ days after last dose ≤ 99
24	Off Treatment 24-weeks b	168	100 ≤ days after last dose ≤ 252
48	Off Treatment 48-weeks b	336	253 ≤ days after last dose ≤ 350

a Last dose for patients permanently discontinuing study drug prior to Week 100 Assessments that occur on the date of last dose or less than 14 days after last dose are considered on treatment

b The off-treatment values indicate the value closest to the date of last dose. Results are summarized by Year 1, Year 2, and overall.

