##### **3.1.2. Phase 3 – Year 2 Endpoints**

###### **3.1.2.1. Primary Endpoints**

- Change from baseline in eGFR at Week 100
- Safety assessments through Week 104

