### 4.1. Summary of Study Design

The Phase 3 portion of the 402-C-1603 trial is a double-blind, randomized, placebo-controlled study designed to evaluate the safety and efficacy of bardoxolone methyl up to 30 mg in patients with Alport syndrome. Patients in Phase 3 are randomized 1:1 to receive bardoxolone methyl or placebo. Randomization is stratified by screening urine albumin to creatinine ratio (ACR). Patients randomized to placebo remain on placebo throughout the study, undergoing sham titration.

Adult patients ( $\geq 18$  years of age) receiving bardoxolone methyl start with once-daily dosing at 5 mg. They dose-escalate to 10 mg at Week 2, to 20 mg at Week 4, and then to 30 mg at Week 6 (only if baseline ACR  $> 300$  mg/g) unless contraindicated clinically and approved by the medical monitor. Patients under the age of 18 receiving bardoxolone methyl start dosing at 5 mg every other day during the first week; they begin once-daily dosing with 5 mg during the second week of the study, and then continue with once-daily dosing following the same aforementioned dose-titration scheme based on baseline ACR at Weeks 2, 4, and 6. Dose de-escalation is permitted during the study if indicated clinically; subsequent dose re-escalation is also permitted to meet the dosing objective of the highest tolerated dose.

All patients receive study drug from Day 1 to Week 48. Patients do not receive study drug treatment during a 4-week withdrawal period (between Weeks 48 and 52). Patients re-start study drug treatment at Week 52 at the same dose level that they received prior to the withdrawal period (maintaining the originally randomized treatment group) and continue study drug treatment through Week 100. A follow-up visit occurs at Week 104 (4 weeks after the last dose). The Data Monitoring Committee (DMC) performs quarterly reviews of unblinded data for safety throughout Phase 3 and will evaluate the initial Year 1 results as described in Section 8.1.

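### The off-treatment safety windows end 350 days after last dose while follow-up runs to Day 728, so by-visit safety tables omit two to five of the five Year 2 visits of patients who stopped drug in Year 1

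*SAP*

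**What the plan says.** SAP Section 6.5.4 uses the study-day windows of Table 3 for safety only while the patient is on drug. It then changes the rule: "Once a patient permanently discontinues study treatment, safety data are summarized according to time since last dose as defined in Table 4". Section 6.5.4.1 applies Table 4 to clinical laboratory evaluations, vital signs and ECGs, and Section 10 repeats that routing. The last two rows of SAP Table 4 are "100 ≤ days after last dose ≤ 252" (24 weeks, target 168) and "253 ≤ days after last dose ≤ 350" (48 weeks, target 336). No row follows, and there is no rule for later values.

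Stopping drug does not end follow-up. Section 6.5.4.1 says of patients who stop before Week 100 that they "are asked to resume the planned assessments according to the study schedule in the protocol". In the schedule of assessments (SAP Table 2), the Year 2 visits are Weeks 64, 76, 88, 100 and 104, at Days 448, 532, 616, 700 and 728. The Year 2 primary endpoints in Section 3.1.2.1 include "Safety assessments through Week 104".

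The COVID-19 addendum to the SAP has its own Tables 3 and 4, which change the Week 100 and Week 104 windows. It leaves the off-treatment safety table of the SAP as it was.

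**The concern.** Read together, these rules ask patients to provide values that no by-visit safety table can hold. Once a patient has stopped for good, Table 3 no longer applies to the planned safety summaries, and Table 4 ends less than a year after the last dose. A patient who stops in Year 1 can be followed for well over a year after that.

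At stake is the by-arm description of late off-drug safety: laboratory tests other than eGFR, vital signs and ECGs. One eGFR value is also affected. Note g to SAP Table 3 and note a to the addendum's Table 4 treat Week 104 as missing for a patient not dispensed drug in Year 2. That patient's observed Week 104 eGFR therefore enters neither the Week 104 efficacy analysis nor any off-treatment safety row.

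**Working it through.** The 350-day limit is stated in the SAP and not derived, so there is no figure of the plan to reproduce. The check is window arithmetic.

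**Inputs.** Year 2 visit days V = 448, 532, 616, 700, 728 (SAP Table 2). Year 1 stop days L = 1 to 336, because "All patients receive study drug from Day 1 to Week 48" (SAP Section 4.1) and 48 × 7 = 336. Days after last dose = visit date − date of last dose (SAP Section 6.5.2), which is V − L.

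**Condition.** A visit is beyond Table 4 when V − L > 350, that is, when L < V − 350.

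- Week 64: 448 − 350 = 98, so lost for L ≤ 97
- Week 76: 532 − 350 = 182, so lost for L ≤ 181
- Week 88: 616 − 350 = 266, so lost for L ≤ 265
- Week 100: 700 − 350 = 350, so lost for L ≤ 349, which covers every Year 1 stop
- Week 104: 728 − 350 = 378, so lost for L ≤ 377, which also reaches stops very early in Year 2

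**Result by stop day.**

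| Last dose on | Year 2 visits beyond 350 days |
|---|---|
| Days 1-97 | 5 of 5 |
| Days 98-181 | 4 of 5 |
| Days 182-265 | 3 of 5 |
| Days 266-336 | 2 of 5 (Weeks 100 and 104) |

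**Visit tolerance.** With the latest Year 1 stop (Day 336) and the earliest permitted visits (Day 700 − 3 = 697 and Day 728 − 6 = 722), the distances are 697 − 336 = 361 and 722 − 336 = 386. Both exceed 350, so early attendance does not rescue Week 100 or Week 104.

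**ECGs.** SAP Table 2 schedules Year 2 ECGs only at Weeks 100 and 104. For a Year 1 stopper, all of them are beyond Table 4.

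**Average, under an assumption.** If stop days were uniform over Days 1-336, the share of Year 2 visits removed would be (97×5 + 84×4 + 84×3 + 71×2) / (336×5) = 1215/1680 = 72%. The documents do not give the timing of stops. By stop day, the share ranges from 40% (2 of 5) to 100%.

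**A second, separate loss.** When several values fall in one window, "the one that is closest to the protocol-scheduled time point (i.e., target) is used for the purposes of data analysis and summary". A stop on Day 336 puts Weeks 64, 76 and 88 at 112, 196 and 280 days. The first two share the 100-252 row, so only Week 76 (28 days from target 168, against 56 for Week 64) is tabulated. That loss comes from the one-value rule, not from the 350-day limit, and is not counted above.

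**The case against.** The strongest reply is that little of consequence is lost.

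- **eGFR.** Efficacy analyses through Week 100 use Table 3 study-day windows whether or not the patient is on drug (Section 6.5.4). The Year 2 MMRM includes Weeks 64, 76, 88 and 100 (Section 8.8.1), with arm comparisons at each (Section 9.1.1.1). Off-drug eGFR at four of the five Year 2 visits is thus analysed by arm. This stands, and it limits the point to the other measures and to the Week 104 eGFR.
- **Other outputs.** Off-treatment adverse events have their own tables (Section 10.1). Laboratory and ECG threshold counts at any time in the study do not depend on these windows (Sections 10.5.2, 10.5.2.1 and 10.8). All values are listed (Section 6). This stands too. A reader might infer that the late values survive only in listings, or that the Week 104 safety endpoint is not delivered for these patients. Neither follows.
- **Model-based summaries.** Section 10 allows some safety parameters to be modelled on Table 3 windows. These are optional, so they do not close the gap.
- **Kidney harm.** A reader might link the gap to Section 2.1, where a decline after withdrawal could point to harm. That text concerns the 4-week withdrawal analysis, not values almost a year or more off drug.
- **Footnote b of SAP Table 4.** It plans summaries by Year 1, Year 2 and overall. Year 2 stoppers, and Year 2 values of Year 1 stoppers within 350 days, can still fill a Year 2 summary, so the footnote is not contradicted.
- **Numbers.** The count of Year 1 stoppers is not given. Section 7.1 accepts follow-up by phone, which yields no laboratory, vital-sign or ECG value. The affected group may be small.

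What the reply does not supply is a by-visit window for values after 350 days.

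**Conclusion.** The gap is real but narrow. For patients who stop in Year 1 and stay in in-person follow-up, the by-visit off-treatment tables always omit Weeks 100 and 104, and with them every scheduled Year 2 ECG. They omit two to all five of the Year 2 laboratory and vital-sign visits, depending on the stop day. Stops up to Day 377 lose Week 104.

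It would be too strong to say that most or all Year 2 values are lost for every Year 1 stopper. For stops on Days 266-336 the cutoff removes 2 of 5. Nor do the documents say why patients stop, so nothing can be inferred about tolerability.

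The result rests on visits held at their scheduled days and on the literal routing to Table 4. How many patients it touches cannot be computed from the documents. These are descriptive tables without formal testing, so no efficacy conclusion depends on them. The change is still worth making, because the plan asks for these values and then gives them no place in the by-visit summaries.

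**What to change.** Extend SAP Table 4 to the end of follow-up with contiguous rows and the same by-arm summaries, for example:

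| Row | Target (days after last dose) | Window |
|---|---|---|
| 48 weeks | 336 | 253-378 |
| 60 weeks | 420 | 379-462 |
| 72 weeks | 504 | 463-546 |
| 84 weeks | 588 | 547-630 |
| 96 weeks | 672 | 631 or more |

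The cut points lie midway between targets, for example (336 + 420)/2 = 378. Every scheduled value after 350 days then has a row; the longest possible distance is 728 − 1 = 727 days.

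The one-value-per-window rule still applies, so two visits in one row give one tabulated value. With closest-to-target selection and no split by year, the Year 2 visits tabulated for stops on Days 28, 84, 168, 252 and 336 rise from 0, 0, 1, 2 and 2 to 4, 5, 4, 4 and 3. For the Day 336 stop, Week 100 (364 days, 28 from target) takes the 48-week row from Week 88 (280 days, 56 from target), and Week 104 (392 days) goes to the 60-week row. The widened 48-week row can thus displace a value that it now holds.

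The cost is one changed row, four new rows and the matching table shells. No new data are needed. The downside is that the added rows will hold few patients, so the SAP should show the number of patients in each.
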